### **3. SAMPLE SIZE JUSTIFICATION**

The sample size is based on clinical feasibility and adequate size to characterize safety in the study population, without consideration for statistical power.

Patients who are randomized but do not receive study drug for any reason may be replaced. Patients who discontinue treatment early for reasons other than safety (e.g. withdrawal of consent, lost to follow-up, patient relocated) may also be replaced.

### **4. GENERAL STATISTICAL METHODS**

#### **4.1. Reporting Conventions**

Individual patient data obtained from electronic case report forms (eCRFs), central laboratories, external sources, and any derived data will be presented in data listings by patient. The primary data source will be used for all analyses. All data listings that contain an evaluation date will contain a relative study day. Pre-treatment and on-treatment study days are numbered relative to the day of the first dose of study drug which is designated as Day 1. The preceding day is Day -1, the day before that is Day -2, etc.

All outputs will be incorporated into Microsoft Word rich text format (.rtf) files, sorted and labeled according to the International Council for Harmonisation (ICH) E3 guideline, E3 Structure and Content of Clinical Study Reports, and formatted to the appropriate page size(s), font type, and font size according to Food and Drug Administration (FDA) guidance of Portable Document Format Specifications.

For categorical variables, summary tabulations of the number and percentage of patients within each category of the parameter will be presented. Percentage calculations will be based on non-missing data, unless otherwise specified. If there are missing values, the number missing will be presented, but without a percentage. Percentages are rounded to 1 decimal place, unless otherwise specified.

For frequency counts of categorical variables, categories whose counts are zero will be displayed for the sake of completeness. For example, if none of the patients discontinue due to “Lost to Follow-up,” this reason will be included in the table with a count of 0. Percentages will be

presented to 1 decimal place, with the exception of 0, which will be presented without percent, and 100, which will be presented without decimal places. Values less than 0.1% will be presented as “<0.1%.” Values less than 100% but greater than 99.9% will be presented as “>99.9%.”

For continuous variables, the number of patients, mean, standard deviation (SD), median, 25th (Q1) and 75th (Q3) percentiles, minimum, and maximum values will be presented. The precision of summary statistics, unless otherwise specified will be as follows: mean, median, Q1, and Q3 to 1 more decimal place than the raw data, SD to 2 decimal places more than the raw data, and minimum and maximum to the same decimal places as the raw data. In general, the number of decimal places should not exceed 3 decimal places unless appropriate.

For log-normal data (e.g., the PK parameters of area under the concentration-time curve [AUC] and maximum observed concentration [Cmax]), the geometric mean and geometric coefficient of variation (CV%) will also be presented. The precision of descriptive statistics will be as follows: mean, median, Q1, and Q3 to 1 more decimal place than the raw data, SD to 2 decimal places more than the raw data, the minimum and maximum to the same number of decimal places as the raw data, geometric mean to 3 significant figures, and geometric CV% to 1 decimal place. The PK parameters Tmax, Tmin, Tlast, and t1/2 will be presented to 1 decimal place and all other plasma and urine PK parameters will be presented to 3 significant figures.

Confidence intervals (CIs) will be provided and will be rounded to 1 decimal place, unless otherwise specified, in the table and listing shell. A full set of summary statistics will only be presented if 3 or more values are available. If there are less than 3 values, only the min, max, and N will be presented. The other summary statistics will be denoted as not calculated (NC).

For tables where rounding is required, rounding will be done to the nearest round-off unit. For example, when rounding to the nearest integer, values  $\geq$ XX.5 will be rounded up to XX+1 (e.g., 97.5 will round up to 98), while values <XX.5 will be rounded down to XX (e.g., 97.4 will round down to 97).

All statistical tests comparing groups will be conducted at the 2-sided, 0.05 level of significance, unless otherwise specified. Summary statistics for each treatment group will be presented, as well as two-sided 90% and 95% CIs comparing groups will be provided.

Other general programming specifications are provided in [Appendix 1](#).

## 4.2. Computing Environments

All descriptive statistical analyses will be performed using SAS software Version 9.4 or higher, unless otherwise noted.

Plasma PK and PD parameters for TERN-201 will be estimated using non-compartmental methods with Phoenix WinNonlin® Version 8.3 or higher.

Medical history and AEs will be coded using Medical Dictionary for Regulatory Activities (MedDRA) version 24.0. Concomitant medications will be coded using World Health Organization Drug Dictionary (WHODD), B2 Enhanced March 2021.

Study Data Tabulation Model (SDTM) and Analysis Data Model (ADaM) datasets will be prepared using Clinical Data Interchange Standards Consortium (CDISC) SDTM

Implementation Guide (IG) Version 3.3, ADaM Version 2.1, and CDISC ADaM IG Version 1.2 including most current occurrence and time to event IGs.

#### 4.3. Partial Dates

Imputation of partial adverse event and concomitant medication dates are specified in [Appendix 2](#), respectively.

All data recorded on the case report form will be included in data listings.

#### 4.4. Data Conventions

The precision of original measurements will be maintained in summaries, when possible.

Quantitative safety laboratory tests containing less than (<) and greater than (>) symbols are test results that are below and above quantifiable limits, respectively. In order to retain these values for analysis purpose, the following will be imputed and stored within the analysis datasets:

- For values with <, the imputed value will be the numeric portion  $\times 0.9$ .
- For values with >, the imputed value will be the numeric portion  $\times 1.1$ .

PK and PD imputation of values below the limitation of quantitation (BLQ) are specified in [Section 8.7.1](#) and [Section 8.8.1](#), respectively.

Variables with a non-normal distribution that impacts the interpretation or validity of the planned analysis may have a data transformation applied (e.g., ln,  $\log_{10}$ ).

#### 4.5. Standard Calculations

Variables requiring calculation will be derived using the following formulas:

- Days – A duration expressed in days between one date (*date1*) and another later date (*date2*) will be calculated using the following formulas:
  - duration in days =  $date2 - date1 + 1$ , where  $date1 \geq$  first administration date
  - duration in days =  $date2 - date1$ , where  $date1 <$  first administration date
- Months – A duration expressed in months is calculated as the number of days divided by 30.4375
- Years – A duration expressed in years between one date (*date1*) and another date (*date2*) is calculated using the following formulas:
  - duration in years =  $(date2 - date1 + 1)/365.25$ , where  $date1 \geq$  first administration date
  - duration in years =  $(date2 - date1)/365.25$ , where  $date1 <$  first administration date
- Body Mass Index (BMI) – BMI is calculated using height (cm) and weight (kg) using the following formula:
$$BMI \text{ (kg/m}^2\text{)} = \text{weight (kg)} / ([\text{height (cm)} / 100]^2)$$

- Change (CHG; equivalent to absolute change for liver fat content [LFC]) – Change will be calculated as:

Change = later value – earlier (i.e., baseline) value

- Percent change (PCHG; equivalent to relative change for LFC) – Percent change will be calculated as:

Percent change = ([Change] / earlier [i.e., baseline] value) × 100

#### 4.6. Treatments

**Table 3** presents how the dose groups will be presented on TFLs as treatment groups, including the order. If Part 2 enrolls, placebo patients from Part 1 and Part 2 will be pooled.

**Table 3: Treatment Group Labels and Ordering**

Treatment Group Label	Order on TFLs
Placebo	1
4 mg	2
10 mg	3
20 mg	4
All TERN-201	5
Overall (where specified)	6

All TERN-201 will not be included on efficacy, PK, or PD tables. Screen failures will be presented on by-patient listings where data is available.

#### 4.7. Visits

##### 4.7.1. Windows

Each visit will be denoted by its visit “Week”. The first dose day is denoted as Day 1. In data listings, the relative study day of all dates from first dose will be presented.

In the event of unscheduled visits or early treatment termination (ET) assessments, these will be reassigned to a scheduled visit for analysis purposes according to **Table 4** for on treatment assessments. If multiple assessments occur within a single visit window, after reassignment of unscheduled visits and ET assessments, the assessment closest to the target day of the visit window will be used in the analysis. If there is a tie, the later assessment will be used in the analysis.

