12-lead ECG	X	X			X		X			In addition to the scheduled timepoints, perform ad-hoc ECG in the instance of patient-reported symptoms considered potentially cardiac in nature such as chest pain/pressure, palpitations, dizziness, shortness of breath, or report of patient recently seeking medical care for such symptoms (e.g., emergency room visit); obtain cardiology consult based on the clinical judgement of the Investigator.

	Screening	Treatment Period ^a						ET ^b	Follow-Up ^c	Notes
Visit	Screening	Week 0	Week 2	Week 4	Week 6	Week 8	Week 12		Week 16	
Study Day	-42 to Day -1	Day 1	15	29	43	57	85		113	Visit windows post-randomization through Week 12: \pm 3 days from the specified study day. Visit window Week 16: 1 week prior/+2 days from the specified study day.
Transient Elastography	X						X	X		A historical transient elastography report within 3 months of Screening may be used to determine eligibility for this study. See inclusion/exclusion criteria for details.
MRI cT1 ^g	X				X		X	X		A Screening MRI cT1 may proceed on the basis of the initial ALT and AST levels at Screening, given all other eligibility criteria are met, but randomization should not occur prior to confirmation of ALT and AST stability, as necessary. An MRI cT1 should be performed at ET if the patient has had at least 4 weeks of dosing.
Dispense Study Drug ^h		X		X		X				Study drug will be assigned via the IWRS. Patients will be supplied with enough study capsules for 4-week use.
Drug Accountability			X	X	X	X	X	X		
Lifestyle Counseling		X	X	X	X	X	X	X	X	Guidance should be provided on key elements of a healthy lifestyle at each visit including diet, exercise, weight loss, and avoidance of alcohol per standard of care management for a NASH patient population.

	Screening	Treatment Period ^a							ET ^b	Follow-Up ^c	Notes
Visit	Screening	Week 0	Week 2	Week 4	Week 6	Week 8	Week 12		Week 16		
Study Day	-42 to Day -1	Day 1	15	29	43	57	85		113		Visit windows post-randomization through Week 12: \pm 3 days from the specified study day. Visit window Week 16: 1 week prior/+2 days from the specified study day.
Adverse Events Review	X	←=====→							X	X	After informed consent but prior to initiation of study drug, all AEs and SAEs related to protocol-mandated procedures should be reported. All AEs and SAEs, regardless of cause or relationship, will be collected from the start of study drug through the Follow-Up Period.
Concomitant Medications Review		←=====→							X	X	

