Patients who meet NASH entry criteria based on a liver biopsy (Inclusion Criteria #4) should still undergo transient elastography at Screening to enable assessment of change from baseline in stiffness by transient elastography.

Transient elastography will also be conducted at Week 12, and at ET.

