**Table 4: Treatment Period Visit Windows**

Target Scheduled Visit	Target Study Day a	Analysis Window Study Day a	
		Low	High
Baseline b	1	See Section 4.7.2	
Week 2	15	2	22
Week 4	29	23	36
Week 6	43	37	50
Week 8	57	51	71
Week 12 c	85	72	92 c

a Study day will be calculated from first dose of study drug.  
b Baseline is defined in [Section 4.7.2](#).  
c LFC and cTI by MRI will have no upper limit on Week 12.

The follow up visit (Week 16) will not be windowed. As described in [Section 8.10.3.1](#), sensitivity analyses will be conducted including only Week 16 assessments which are at least 22 days from last dose.

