#### **8.10.1.1. Corrected T1 (cT1)**

cT1 related to the amount of extracellular fluid present in the liver parenchyma. cT1 is derived from T1 and T2\* maps. T1 is a measure of the longitudinal (spin-lattice) relaxation time, measured in milliseconds (msec), of a given substance. The T1 of a tissue depends on its free water content, which relates to the proportion of the extracellular fluid in the tissue.

Proton-dense tissues with a low water content, such as fat, have very short T1 values, while tissues with a high water content, such as muscle and the spleen have much longer T1 values. When tissue is inflamed or scarred (fibrotic), changes in the structural organization of the tissue, due to tissue remodeling, mean that the water content increases, leading to longer T1 values.

cT1 is measured in milliseconds (msec). The cT1 metric is calculated from all pixels with whole slice ROIs placed on the cT1 parametric map. The cT1 metric is displayed as a median and IQR, the median will be used in all analyses.

Analyses of cT1 will be based on the Efficacy Analysis Set. Descriptive statistics of the cT1 values, change from baseline, and percent change will be summarized by treatment group and visit.

Analyses of change (and separately percent change) from baseline will be carried out using an ANCOVA model at each scheduled visit with change (and separately percent change) from baseline as the dependent variable including treatment group and randomization strata as fixed effects and baseline as a covariate.

The estimates of least-square (LS) means, standard errors (SE), and 90% and 95% CIs will be presented by treatment group. Estimates of the LS mean difference for each pairwise comparison will be presented with associated the standard error of the difference, and 90% and 95% CIs of the difference.

The primary analysis of change (and separately percent change) at Week 12 will be carried out using available observed data only, without imputation for missing data. The same ANCOVA

model will be used to present the last on treatment value for Week 12, to be labelled as “Week 12/End of Treatment”. For patients who complete Week 12, the Week 12 value will be used. For patients who do not complete treatment, the last value on treatment will be used.

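### SAP Table 4 puts every test on one visit grid, so many early-termination MRI, elastography, fibrosis-marker and urine values land at visits where that test is not planned, and the Week 12 MRI window has no limit tied to last dose

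*SAP*

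**What the plan says.** SAP 4.7.1 sets one rule for all tests: in the case of "unscheduled visits or early treatment termination (ET) assessments, these will be reassigned to a scheduled visit for analysis purposes according to" Table 4. That sentence goes on to confine the rule to on-treatment assessments, a term the SAP does not define. If several values share a window, "the assessment closest to the target day of the visit window will be used in the analysis". Table 4 covers Weeks 2, 4, 6, 8 and 12, and "Study day will be calculated from first dose of study drug". Its only test-specific exception is footnote c: "LFC and cTI by MRI will have no upper limit on Week 12". For the off-drug visit, "The follow up visit (Week 16) will not be windowed".

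The Protocol 1.3 schedule is sparser for several tests. On treatment, MRI, NASH/fibrosis biomarkers and urinalysis (which includes UPCR and UACR) are done at Weeks 6 and 12, plus ET. For MRI, "An MRI cT1 should be performed at ET if the patient has had at least 4 weeks of dosing". For elastography, Protocol 8.1.8 says: "Transient elastography will also be conducted at Week 12, and at ET". Inflammation biomarkers are drawn at every treatment visit and at ET.

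In SAP 8.10.1.1 the analysis of cT1 change "will be carried out using an ANCOVA model at each scheduled visit with change (and separately percent change) from baseline". SAP 4.7.3 defines End of Treatment as the Week 12 value, scheduled or windowed. Failing that, it takes the last value dated no later than the last dose.

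**The concern.** The protocol asks patients who stop early to have an extra MRI, elastography and samples. The likely purpose is to keep some post-baseline information on them. If the window rule labels those values with a visit at which nobody else has the test, they reach neither the Week 6 nor the Week 12 comparison with placebo. An ANCOVA with treatment, stratum and baseline terms cannot usefully be fitted to one or two stray scans.

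The open-ended MRI window raises the opposite problem. A scan taken long after the last dose could be analysed as an observed Week 12 value, which would tend to dilute a drug effect that fades off treatment. It would also become that patient's End of Treatment value, ahead of a genuine on-treatment Week 6 scan. With about 10 placebo patients in Part 1, one scan is 1/10 of that arm (1/20 of pooled placebo if Part 2 enrols).

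**Working it through.** **1. Reproduce Table 4.** Target days are 15, 29, 43, 57 and 85. Upper limits as midpoints: (15+29)/2 = 22; (29+43)/2 = 36; (43+57)/2 = 50; (57+85)/2 = 71. The last limit is 85+7 = 92. All match, so the grid is built on the full five-visit schedule.

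**2. Map ET days before the Week 12 window (to Day 71).** Window lengths are Week 2 = 21 days, Week 4 = 14, Week 6 = 14 and Week 8 = 21, total 70. For MRI, I take four weeks of dosing to mean ET from Day 29, so Week 4 contributes Days 29-36 = 8 days and the total is 8+14+21 = 43.

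| Test | Planned visits | ET days labelled with an unplanned visit | Share |
|---|---|---|---|
| MRI (cT1, PDFF) | 6, 12 | 8 (Week 4) + 21 (Week 8) = 29 of 43 | 67% |
| NASH/fibrosis biomarkers, UPCR/UACR | 6, 12 | 21+14+21 = 56 of 70 | 80% |
| Elastography | 12 | 70 of 70 | 100% |
| Inflammation biomarkers | all | 0 of 70 | 0% |

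Starting ET MRI at Day 28 gives 30 of 44 (68%). Extending the count to Day 84 adds 13 correctly placed days: MRI 29/56 = 52%, NASH/fibrosis and urine 56/83 = 67%, elastography 70/83 = 84%.

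**3. Does End of Treatment recover the value?** Suppose the last dose is on Day 57 and the ET MRI on Day 60. Table 4 labels the scan Week 8. There is no Week 12 value, so 4.7.3 falls back to values dated no later than Day 57. The ET scan, 60-57 = 3 days later, fails, and the Week 6 scan is used. The protocol places the ET visit promptly after discontinuation but with no day limit, so this will be the usual sequence. For elastography there is no planned on-treatment value before Week 12, so the ET value is normally the only post-baseline one, and the fallback excludes it.

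**4. Off-drug values.** By Table 4 and footnote c:
- Last dose Day 43, MRI Day 113: 70 days off drug, labelled Week 12.
- Last dose Day 85, MRI Day 140: 55 days off drug, labelled Week 12.
- Last dose Day 43, MRI Day 60: labelled Week 8, not Week 12.
- Last dose Day 43, any other test on Day 92: 49 days off drug, labelled Week 12.

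No window is tied to last dose; footnote c only makes this open-ended for MRI.

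**5. What test-specific midpoints would do.** For tests planned at Weeks 6 and 12, (43+85)/2 = 64, so Week 6 ends on Day 64 and Week 12 starts on Day 65. Of the 29 misplaced MRI days, 8 (Days 29-36) and 14 (Days 51-64) move to Week 6, and 7 (Days 65-71) move to Week 12. For Days 51-64 a patient will normally already have a Week 6 scan near Day 43, which wins as the closer value. New windows alone therefore bring in ET scans from 8+7 = 15 of the 29 days. The other 14 depend on the End of Treatment rule, so both changes are needed.

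**The case against.** The strongest reply is that the plan already covers early stopping. SAP 8.2 and 8.10.1.1 add a Week 12/End of Treatment analysis using the last on-treatment value, and the primary analysis is meant to use observed data only. A patient who stopped before Day 72 has no Week 12 observation, so leaving that patient out of Week 12 is consistent. That stands for the by-visit Week 12 analysis. It does not stand as a rescue: the definition in 4.7.3 excludes the typical ET value, and the sections on elastography (8.10.2) and NASH/fibrosis biomarkers (8.10.4) specify observed data only.

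Three stronger readings are tempting, and the documents do not support them.

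- *Any MRI after stopping counts as Week 12.* Footnote c removes only the upper limit; the Day 72 lower limit remains. The on-treatment restriction in 4.7.1 may also exclude off-drug scans. No MRI is planned at Week 16, so such scans would be late or unscheduled, and the open limit may simply be meant to keep delayed Week 12 scans. The fault is an undefined term in tension with a footnote.
- *Most ET data are lost.* ET MRI, NASH/fibrosis and urine values on Days 37-50, and those in the Week 12 window, are labelled with a planned visit. Inflammation biomarkers are never misplaced.
- *Stray Week 4 and Week 8 values will break the dose-response MMRM.* That analysis is framed around Part 2 enrolling, SAP 8.8.4.4 lists fallback covariance structures, and nothing says visit levels without a planned test must be modelled.

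**Conclusion.** The point holds in this form: one grid is applied to tests with different schedules, the End of Treatment fallback does not reliably pick up what the grid misplaces, and the Week 12 MRI window has no limit relative to last dose. The size is 29 of 43 ET days for MRI, 56 of 70 for NASH/fibrosis biomarkers and UPCR/UACR, and all 70 for elastography, counted to Day 71.

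These are shares of calendar days. The documents give no dropout timing, so the number of patients affected is unknown and may be small; patients who stop for non-safety reasons may also be replaced. The result assumes that ET MRI starts about Day 29 and that ET visits usually follow the last dose. Whether off-drug MRIs enter Week 12 depends on how a programmer reads the on-treatment restriction, and two careful programmers could build different datasets. The affected endpoints are exploratory and testing is nominal (SAP 8.6), so the priority is modest. The primary safety endpoint is untouched.

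**What to change.** 1. **Test-specific windows.** Keep Table 4 for tests done at every visit. For MRI, NASH/fibrosis biomarkers and UPCR/UACR, split Week 6 and Week 12 at Day 64/65. Give Week 6 a lower bound that keeps out very early values; the midpoint from Day 1 is (1+43)/2 = 22, so Day 22 or 23. For elastography, analyse ET values in a Week 12/End of Treatment analysis and do not relabel mid-treatment values as Week 12.
2. **Define on treatment** as a pre-specified number of days after last dose, and apply it in 4.7.1, 4.7.3 and 8.10.1.1 so that ET assessments shortly after the last dose qualify for End of Treatment. The documents give no figure for this purpose, so the sponsor should choose and justify one. Counting from last dose is already done elsewhere: the ALT follow-up sensitivity analysis uses at least 22 days.
3. **Make footnote c consistent** with that definition, and keep later MRIs in a sensitivity analysis.

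The cost is one table, one definition and one footnote, with no new data. The downsides are wider Week 6 and Week 12 windows, very early ET samples that are assigned to no visit, and an occasional late MRI moved to a sensitivity analysis. Settle it before Part 1 is unblinded, so that which scans count as Week 12 is not decided with treatment known.

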1.3. Schedule of Activities

	Screening	Treatment Period ^a						ET ^b	Follow-Up ^c	Notes
Visit	Screening	Week 0	Week 2	Week 4	Week 6	Week 8	Week 12		Week 16	
Study Day	-42 to Day -1	Day 1	15	29	43	57	85		113	Visit windows post-randomization through Week 12: ± 3 days from the specified study day. Visit window Week 16: 1 week prior/+2 days from the specified study day.
Procedures										
Written Informed Consent	X									Written informed consent may be obtained via telephone in accordance with Section 10.1.2 . Screening may be initiated via telephone.
Patient Fasting	X	X	X	X	X	X	X	X	X	Patients must be in fasted state for at least 8 hours prior to blood collection and study drug administration, where applicable.
Randomization		X								
Review Inclusion and Exclusion Criteria	X	X								Recheck clinical status before randomization and first dose of study drug.
Demographics	X									Includes age, sex, and race/ethnicity.
Height and Weight	X	X	X	X	X	X	X	X	X	Height and weight are collected at Screening and will be used to calculate BMI for eligibility. Waist circumference is also measured at Screening. Only weight is collected on other days indicated.
Medical History	X	X								Includes details of illnesses and allergies, date(s) of onset, whether condition(s) is currently ongoing, and medication history, including alcohol use.

	Screening	Treatment Period ^a						ET ^b	Follow-Up ^c	Notes
Visit	Screening	Week 0	Week 2	Week 4	Week 6	Week 8	Week 12		Week 16	
Study Day	-42 to Day -1	Day 1	15	29	43	57	85		113	Visit windows post-randomization through Week 12: \pm 3 days from the specified study day. Visit window Week 16: 1 week prior/+2 days from the specified study day.
Physical Examination	X	X	X	X	X	X	X	X	X	A complete physical examination will be performed at Screening and Week 16. A targeted physical examination will be performed at all other visits, as needed.
Vital Signs	X	X	X	X	X	X	X	X	X	Includes temperature, pulse rate, respiratory rate, and blood pressure.
Chemistry ^d	X	X	X	X	X	X	X	X	X	Specific analytes are listed in Appendix 1 . ALT and AST stability may be evaluated prior to randomization per Section 5 . Increased monitoring criteria for elevated ALT and/or AST above $2 \times$ Baseline or above $5 \times$ ULN for < 1 week is outlined in Appendix 3 . Refer to Appendix 5 for the eGFR formula, to be calculated by central lab.
Hematology ^d	X	X	X	X	X	X	X	X	X	Specific analytes are listed in Appendix 1 .

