8.1.7. Clinical Laboratory Assessments

See [Appendix 1](#) for the list of clinical laboratory tests to be performed and the Schedule of Activities for the timing and frequency.

The Investigator must review the laboratory report, document this review, and record any AEs per the guidance in [Appendix 6](#). The laboratory reports must be filed with the source documents.

Clinically significant laboratory shifts, or any clinically significant abnormalities considered possibly related to study drug in the opinion of the Investigator, should be repeated within 48-72 hours and followed to resolution or until stable.

All protocol-required laboratory assessments, as defined in [Appendix 1](#), must be conducted in accordance with the laboratory manual and the Schedule of Activities.

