Appendix 3: Liver Chemistry Increased Monitoring Criteria

[Table 4](#) summarizes requirements for follow-up of liver function test abnormalities.

Table 4 Liver Chemistry Increased Monitoring Criterion and Follow-Up

Criterion	Actions
Elevated ALT and/or AST above 2 × Baseline or above 5 × ULN for < 1 week	
• Patient can continue study drug at the discretion of the Investigator• Repeat measurement of LFTs (including ALT, AST, ALP, and total bilirubin) will be performed within 48-72 hours to confirm the abnormalities and to determine if they are increasing or decreasing. If total bilirubin is increased there should be a reflex to direct and indirect bilirubin.• PT/INR and albumin will be tested when significantly abnormal liver function is observed, and repeated with repeat measurement of LFTs.• Upon confirmation of elevated LFTs, close observation by repeating LFTs every 24 to 72 hours will be initiated immediately.• Frequency of monitoring can be decreased as LFTs decrease at the Investigator's discretion.• The Investigator will collect detailed history information on concomitant symptoms, new medications, drug or alcohol exposure, etc., to identify possible cause of abnormal LFTs.• Close observation on abnormal LFTs will last until the parameters return to baseline, or to a stable level judged by the Investigator.

Note: If one of the following situations occurs and is considered related to the study drug without alternative etiology, study drug may be discontinued at the discretion of the Investigator and the Medical Monitor should be informed (with repeat test performed within 48-72 hours once initial abnormality is detected):
 
• ALT or AST > 8 × ULN• ALT or AST > 5 × ULN for more than 1 week• ALT or AST > 2 × Baseline with the appearance of fatigue, nausea, vomiting, right upper quadrant pain or tenderness, fever, rash, and/or eosinophilia (> 5%)• ALT or AST > 2 × Baseline and total bilirubin > 2 × ULN or INR > 1.5 for more than 1 week, confirmed with a repeat assessment	

Abbreviations: ALP = alkaline phosphatase; ALT = alanine transaminase; AST = aspartate transaminase; INR = international normalized ratio; LFT = liver function test; PT = prothrombin time; ULN = upper limit of normal

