### **8.10.3. Liver Function Tests**

LFTs for efficacy analyses include AST, ALT, and GGT. Descriptive statistics of LFT values, change from baseline, and percent change from baseline values will be presented by treatment group for each visit using the Efficacy Analysis Set.

Change (and separately for percent change) from baseline will be analyzed using the same ANCOVA model presented in [Section 8.10.1.1](#) for each post-baseline and follow up visit using observed data only. Sensitivity analyses using the PP and Treatment Completer Analysis Sets will be presented if the analysis set differs from the Efficacy Analysis Set by more than 10% total.

Assessments of normality will be performed as described in [Section 8.10.1.1](#).

Figures of LS mean ( $\pm$ SE) change from baseline, and percent change from the ANCOVA model will be presented over time by treatment group.

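### SAP 4.7.1 gives a scheduled sample no priority over a repeat ordered because that sample was abnormal, so by-visit laboratory summaries and the exploratory ALT/AST analyses can understate transient elevations (minor)

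*SAP*

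**What the plan says.** SAP 4.7.1 deals with unscheduled and early termination (ET) assessments made on treatment: "these will be reassigned to a scheduled visit for analysis purposes according to" Table 4. If a window then holds more than one assessment, "the assessment closest to the target day of the visit window will be used in the analysis". The tie rule is: "If there is a tie, the later assessment will be used in the analysis". Nothing in the section ranks a scheduled sample above an unscheduled one.

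The protocol determines when a second sample exists:

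- Section 8.1.7: laboratory shifts or abnormalities judged clinically significant "should be repeated within 48-72 hours and followed to resolution or until stable".
- Appendix 3, for ALT or AST above 2 × Baseline or above 5 × ULN: "Repeat measurement of LFTs (including ALT, AST, ALP, and total bilirubin) will be performed within 48-72 hours". Once the elevation is confirmed, "close observation by repeating LFTs every 24 to 72 hours will be initiated immediately".
- Section 1.3: "Visit windows post-randomization through Week 12: ± 3 days from the specified study day".

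The selected value goes into the by-visit descriptive laboratory summaries (SAP 9.3). It also goes into the liver function ANCOVAs and LS-mean figures of SAP 8.10.3, which are run "for each post-baseline and follow up visit using observed data only".

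**The concern.** A competing sample is not a random extra measurement. It exists mainly because the scheduled value was high. An unremarkable scheduled value triggers no repeat and always keeps its slot. A high value can lose its slot to a repeat taken a few days later, which on average will have moved back toward the patient's usual level. Which value is analysed therefore depends on the result itself.

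The expected effect is to pull by-visit means down where elevations are transient, and to do so more in the arm with more of them. With about 20 patients per active dose and 10 on placebo in Part 1, one or two altered values can move a by-visit mean. Analyses that reuse the windowed ALT or AST value, such as the dose-response models of SAP 8.10.8, inherit the same choice. GGT is less clearly affected, because Appendix 3 does not name it among the repeated tests.

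**Working it through.** The plan gives no figure to reproduce, so the check enumerates the rule.

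**Inputs**

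- Scheduled sample at *d* days from target, *d* = -3 to +3 (Protocol 1.3).
- Repeat at *d + k*, with *k* = 2 or 3 days (48-72 hours; Protocol 8.1.7 and Appendix 3).
- The repeat is selected if |*d + k*| ≤ |*d*|, the equality coming from the tie rule (SAP 4.7.1).
- Distribution of *d*: not in the documents, so varied below.

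**Do both samples fall in one window?** The latest repeat is at +3 + 3 = +6 days. The tightest Table 4 windows end 7 days after target (for example Week 4: target Day 29, window Days 23-36). Both samples therefore share a window at Weeks 2, 4, 6, 8 and 12.

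**Which value is used?**

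| Visit day *d* | Scheduled distance | Distance at *k* = 2 | Used | Distance at *k* = 3 | Used |
|---|---|---|---|---|---|
| -3 | 3 | 1 | repeat | 0 | repeat |
| -2 | 2 | 0 | repeat | 1 | repeat |
| -1 | 1 | 1 (tie) | repeat | 2 | scheduled |
| 0 | 0 | 2 | scheduled | 3 | scheduled |
| +1 | 1 | 3 | scheduled | 4 | scheduled |
| +2 | 2 | 4 | scheduled | 5 | scheduled |
| +3 | 3 | 5 | scheduled | 6 | scheduled |

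Only early visits are displaced. Further serial repeats add no displaced visit days, although a later repeat may be the one selected.

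**How often, among spikes that trigger a repeat?** Every distribution here is an assumption.

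| Assumed visit days | *k* = 3 | *k* = 2 |
|---|---|---|
| Uniform over ±3 | 2/7 = 28.6% | 3/7 = 42.9% |
| Triangular (weights 1, 2, 3, 4, 3, 2, 1) | 3/16 = 18.8% | 6/16 = 37.5% |
| 70% on target, 10% on each of ±1, 2.5% on each of ±2 and ±3 | 2.5 + 2.5 = 5% | 5 + 10 = 15% |
| None early | 0% | 0% |
| All early, uniform over -3 to -1 | 2/3 = 66.7% | 3/3 = 100% |

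**If the repeat comes later.** Protocol 7.1 and the note to Appendix 3 time the repeat from detection of the abnormality, and Appendix 1 sends these tests to a central laboratory. If the repeat falls 4 days after the draw, *d* = -3 and -2 are displaced: 2/7 = 28.6%. At 5 days only *d* = -3 is displaced: 1/7 = 14.3% (both uniform).

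**If Week 12 is exempt.** If a repeat after the last dose is not on treatment, four of five visits remain. With equal weights and uniform days the range is 0.8 × 28.6% = 22.9% to 0.8 × 42.9% = 34.3%.

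**Alternative rules.** With scheduled-first selection, displacement is 0% under any distribution. Reversing only the tie rule leaves 2/7 = 28.6% for both *k* = 2 and *k* = 3 (uniform).

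**The case against.** The strongest reply is that this is a prespecified, date-based rule and that safety detection does not rest on it. Much of that stands:

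- Treatment-emergent abnormalities (SAP 9.3.1) count grade worsening at any time after baseline through Week 16. Shift tables (SAP 9.3.3) use the worst post-baseline value. The Hy's rule check (SAP 9.3.2) uses same-draw values whatever their slot. Values meeting the Appendix 3 criteria are flagged in the analysis dataset and listed, and all laboratory data are listed. A reader might infer that spikes are overwritten and a liver signal hidden; the documents do not support that. The value is only not chosen for a by-visit slot.
- A reader might take 29-43% as the share of all laboratory spikes lost. It is not. Spikes below the repeat criteria have no competitor, the visit-day distribution is assumed, and repeats may be timed from detection.
- The direction is not guaranteed. Appendix 3 orders the repeat to see whether values are rising or falling. A sustained or rising elevation gives an equal or higher repeat.
- ALT and AST are exploratory, testing is nominal (SAP 8.6), and SAP 8.10.3 carries a normality check with log transformation and a rank-based fallback. That may blunt the effect of a few extreme values.
- The Week 16 visit is not windowed, so it is outside the rule.

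None of this removes the gap. No other section gives the scheduled value priority, and the by-visit summaries and ALT/AST models do use the selected value.

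**Conclusion.** The point holds at minor severity. As written, the rule makes the value used in SAP 9.3 by-visit summaries and SAP 8.10.3 ALT/AST analyses depend on whether the scheduled result was abnormal, and it tends to understate transient elevations seen at early visits. That conclusion rests on the text alone.

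The size does not. Depending on assumed visit days and repeat timing, displacement among spikes that trigger a repeat runs from 0% if no visit is early, through 5-15% and about 19-38%, to 29-43% for uniform days with a 2-3 day repeat. It is 14-29% for uniform days with a 4-5 day repeat.

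Nor can a bias in U/L be stated. A reader might construct one: two of 20 patients rise from 60 to 180 U/L and repeat at 108, with 36% displaced. The mean change falls from 2 × 120/20 = 12.0 to 2 × (0.64 × 120 + 0.36 × 48)/20 = 9.4, or 22% lower. The proportional loss is simply the displaced share times the fraction of the excess gone by the repeat (0.36 × 0.6 = 0.216). A repeat at 168 gives 0.36 × 0.1 = 3.6%. The patient values are invented, so neither figure is an estimate for this trial.

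**What to change.** In SAP 4.7.1:

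1. State that the scheduled-visit value is used whenever a valid one exists in the window, and that unscheduled, repeat or ET values fill the slot only if the scheduled value is missing. Erroneous values are already excluded under SAP 9.3, so this would not force a bad result into the analysis.
2. State that all values stay in the worst-post-baseline, shift, liver-injury and listing outputs.
3. Say whether a Week 12 repeat after the last dose counts as on treatment. The reassignment is limited to on-treatment assessments, yet the Table 4 window runs to Day 92. The answer also settles the windowed End of Treatment value in SAP 4.7.3.

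The cost is a few lines of SAP text and one sort key in programming. No data are lost.
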